# 1. **BACKGROUND INFORMATION**

## 1.1 **INTRODUCTION**

Basal cell carcinoma (BCC) is the most common type of skin cancer, with almost 3 million cases diagnosed each year in the United States. (Skin Cancer Foundation 2011, Rogers et al 2010) The incidence of BCC is increasing 10% each year worldwide and its prevalence is expected to equal that of all other cancers combined in the near future. (Madan et al 2010)

Though extremely rare, some patients have progressive mutilating metastatic BCC (mBCC) or locally advanced BCC (laBCC), which can be fatal. Most BCCs are not life-threatening, but they are still quite morbid as they commonly occur on the head and neck. Some BCC lesions grow very quickly and are associated with poorer outcomes. Features of these ‘high risk’ BCC (hrBCC) lesions were defined by the National Comprehensive Cancer Network (NCCN) and this hrBCC cohort was highlighted as one of particular concern. (See Appendix 1, NCCN 2011). Since hrBCC tumors are much more common, they actually represent a much bigger public health problem than mBCC or laBCC.

Due to its superior cure rate, Mohs micrographic surgery (MMS) is widely accepted as the gold standard for treatment for the majority of BCC tumors, especially laBCC and hrBCC. (Mikhail and Mohs 1993, NCCN 2011) Even with the utilization of the Mohs tissue preservation technique, surgery can be quite extensive resulting in significant disfigurement, depending on the size and anatomic location of the lesion.

While size of tumor is a predictive factor of patient outcomes, visual examination can frequently be deceiving and local microscopic invasion may be much more extensive than initially thought. In some cases, tumor seen at the skin surface may only represent one fifth of its microscopic spread. (Batra and Kelley 2004) Since many tumors exhibit significant subclinical extension, the resulting surgical defect after tumor clearance can be considerably larger than the presenting lesion, often necessitating complex, costly, and time-consuming repairs, compromising the final cosmetic appearance or function.

Adjuvant therapies aiding in the removal of primary or recurrent tumors could lessen the risk of cosmetic disfigurement by decreasing tumor burden prior to surgery. Topical therapies, such as imiquimod, have been investigated in the past for this purpose. They are not widely used due to concern that the variable penetration of topical therapy may lead to noncontiguous response, leading the clinician to incorrectly believe that the tumor has been completely cleared. (Harting et al 2007) An oral agent, that hypothetically would be distributed to the tumor uniformly, may be better suited for neoadjuvant treatment of BCC prior to surgery. In fact, in selected lesions, oral treatment could possibly even lead to complete eradication of tumor tissue, thereby eliminating the need for surgery altogether. Vismodegib is an orally delivered small Hedgehog pathway inhibitor (HPI) that shows promise in the management of BCC. Vismodegib was granted priority review and was recently approved by the U. S. Food and Drug Administration for the treatment of adults with metastatic basal cell carcinoma or with locally advanced basal cell carcinoma that has recurred following surgery or who are not candidates for surgery, and who are not candidates for radiation.

## 1.2 RATIONALE

Vismodegib has been shown to have an anti-tumor effect on BCC in preclinical and clinical studies. It exerts its effect by blocking the Hedgehog (Hh) pathway directly, disrupting the development of cancers that are due to PTCH mutations or SMO mutations, like those seen in the majority of BCCs. (Lorusso et al 2011, Von Hoff et al 2009) An estimated 90% of BCC tumors have mutations in the Hh signaling pathway, either an inactivation of the PTCH mutation (loss-of function mutation) or an activation of the SMO15 mutation (gain of function), that disrupt normal signaling between cells and lead to a proliferation of basal cells and the development of BCC. (Rubin and De Sauvage 2006, Hopper and Scott 2006) For this reason, inhibiting the Hh signaling pathway has been identified as a therapeutic target in the treatment of BCC.

Though many BCCs possess the same mutation in the Hh pathway, BCC is a very heterogeneous tumor type when considering all of the known histologic subtypes. Twenty-three subtypes of BCC have been recorded in the literature, but for practical purposes these have been combined and three subtypes (infiltrative/morpheaform, nodular and superficial) are used clinically. (Sexton et al 1990, Wade and Ackerman 1978, Rippey 1998) The most common type of BCC is nodular (70%). (Weedon 2009, Mosterd et al 2011) Superficial subtypes comprise around 10-15% of BCCs. About 10-15% of BCCs are categorized as infiltrative/morpheaform subtype for clinical management and considered to be an “aggressive” subtype of BCC. Infiltrative BCCs and morpheaform BCC have different appearances histologically, but are considered together for management due to their similar aggressive clinical course.

Histologic features are well known to impact tumor biologic behavior and response to treatment. Treatment options for BCC are often curative when considering clinical and histologic features, the latter a more powerful prognostic factor with laBCCs and hrBCCs. (Walling et al 2004) For example, it is well recognized that infiltrative/morpheaform tumors are associated with increased rates of recurrence and poorer prognosis since their tumor characteristics make it difficult to obtain clear margins during surgery. (Walling et al 2004) These BCC subtypes frequently have tumor nests outside of the tumor bulk. During surgery, tumor remnants may go undetected by conventional means and continue to grow. If a histological response to vismodegib in aggressive subtypes can be demonstrated pre-operatively, clinicians may possess greater confidence that all tumor nests have been eradicated and clear margins have been obtained during surgery, leading to improved patient outcomes. Conversely, superficial BCCs are considered to have non-aggressive tumor behavior and are also more likely than other subtypes to be located on the low-risk locations of the trunk and extremities. (Weedon 2009) These tumors, which typically undergo simple excisions, nonetheless can require significant circumferential margins of normal tissue to ensure complete removal, again impacting cosmesis, function and or cost.

It is unknown if BCC histologic subtype impacts tumor response to vismodegib. Data from previous studies, where inclusion was open to all subtypes of basal cell skin cancer, is predominantly based on nodular subtype. Most currently recruiting studies investigating vismodegib in BCC do not specify a tumor subtype for inclusion, but if one is specified for inclusion, it is nodular subtype only. (ClinicalTrials.gov Identifier NCT01201915) No previous or ongoing studies have stipulated inclusion of other histological subtypes of BCC.

The goal of this study is to identify the cohorts of patients that will most likely benefit from treatment with vismodegib. In the new era of cancer therapeutics, matching treatment modality with specific tumor features contributes to better patient outcomes. This investigation will assist in providing a greater understanding of the efficacy of vismodegib in BCCs of aggressive subtypes and of other histologic subtypes. This study may provide better guidance for targeted, individualized information about a patient's unique tumor biology and optimize management of BCCs in our patients.

### 1.3 POTENTIAL RISKS AND BENEFITS

The safety, preliminary efficacy, and pharmacokinetics of vismodegib in mBCC and laBCC were assessed in an open-label, multicenter, two-stage Phase I trial. Patients with solid tumors refractory to standard therapy were treated until disease progression, intolerable toxicities, or withdrawal from the study. Thirty-three patients with mBCC or laBCC were included in analysis and followed over a 20-month period. Assessment using the RECIST criteria version 1.0 was completed if tumors had radiologically measurable disease. Otherwise, pre-defined clinical response measures were employed. An overall response rate of 58% was observed. (Von Hoff et al 2009) The most common response, in 17 of 33 cases, was partial response. Complete response was seen in 2 cases. Stable disease was observed in 12 cases. (Von Hoff et al 2009) No dose-limiting toxic events or grade 5 events were observed with a single grade 4 adverse event (asymptomatic hyponatremia) reported. The more significant and frequent adverse events were GI related with dysgeusia and muscle spasm reported.

Further evidence of the efficacy of vismodegib in the treatment of BCC was shown in the pivotal ERIVANCE trial, a Phase II single-arm, non-randomized trial of single-agent vismodegib at 150 mg/day to progression or intolerance with 104 patients enrolled: (33 mBCC, 71 LA BCC). The study met its primary endpoint overall response rate (ORR) by an independent review facility (IRF) and showed shrinkage of tumors in a pre-defined percentage of patients. A preliminary safety assessment showed the most common adverse events were consistent with previous experience with vismodegib. The most common adverse events were muscle spasms, hair loss, altered taste sensation, weight loss, fatigue, nausea, decreased appetite and diarrhea. A detailed safety assessment is ongoing.

Therapy with vismodegib has the potential to significantly decrease morbidity of the patients' BCC either through complete clearance of tumor or by substantially decreasing the morbidity of surgery. Though BCC expected to respond favorably to treatment with vismodegib, surgical excision by MMS will occur within 6 months of initial consultation; this study will not adversely affect the current standard of care in the management of BCC in non-responders.

In a recent Phase 2 trial, vismodegib was also reported to slow the development of BCCs in patients with Basal Cell Nevus Syndrome (BCNS), a rare genetic disorder which causes patients to develop hundreds of large BCCs. (Tang et al 2011). Further studies are needed, but vismodegib may slow the progression of BCC in patients without BCNS.

## 2. STUDY OBJECTIVES

### 2.1 PRIMARY OBJECTIVES

- To compare the efficacy of vismodegib in various histologic subtypes of high risk and/or locally advanced basal cell skin cancer

### 2.2 SECONDARY OBJECTIVES

- To evaluate the onset of efficacy of vismodegib during 24 weeks of treatment in various histologic subtypes of high risk and/or locally advanced basal cell skin cancer
- To evaluate the safety and tolerability of vismodegib over 24 weeks of treatment in subjects with high risk and/or locally advanced basal cell skin cancer
- To evaluate patient reported outcome (PRO) measures during 24 weeks of treatment with vismodegib in subjects with high risk and/or locally advanced basal cell skin cancer

## 3. STUDY DESIGN

This is a Phase 2B two-site, open-label, nonrandomized 24-week study of the efficacy and safety of vismodegib (150 mg PO daily) in subjects with high risk and/or locally advanced basal cell carcinoma. A total of 36 subjects with infiltrative/morpheaform, nodular, or superficial BCC will be enrolled in the study. Each subtype group will have a minimum of 10 subjects. No group will have more than 16 subjects.

At Treatment Initiation Visit (Baseline/Day 1), eligible subjects will begin a 24-week treatment regimen with vismodegib 150 mg daily. Clinical assessments will be performed every 4 weeks during treatment. Intra-treatment tissue histopathologic evaluation will be conducted at Week 12. Subjects will be eligible to discontinue treatment early and enter the Observation period if there is no histologic evidence of tumor on Week 12 pathology specimens. Post-treatment histopathologic evaluation will be performed at Week 24 (End of Treatment visit). Subjects will be eligible to enter the Observation period in lieu of surgery if their target lesion displays complete histologic response on biopsy specimens obtained at Week 24 visit. For subjects with histologic evidence of disease on pathology at Week 24 visit, surgical excision or Mohs surgery on the target lesion will be performed within 4 weeks of the last dose of study drug. Patient Reported Outcomes (PRO) data will be collected at baseline visit, during treatment, end of treatment/early termination visit, surgical visit, and study exit (post-surgery) visit, and at first Observation period visit (when applicable) Safety assessments including adverse event (AE) monitoring and concomitant medications will be performed at each visit.

The rationale for using 24-week treatment schedule was based on previous data from pilot studies. Data from a previous trial of 33 subjects with advanced BCC, demonstrated that 94% (17/18) of responders responded by 24-weeks. (Von Hoff et al 2009) In non-responders, treatment beyond 24 weeks may unnecessarily endanger the patient and allow their basal cell skin cancer to progress potentially negatively affecting clinical outcome.

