At week 12, Intra-treatment tissue histopathologic evaluation will be performed to assess histologic response. For subjects with apparent clinical complete response at Week 12 and no histologic evidence of disease is observed, subjects will enter the observation period and be followed clinically every 3 months up to one year (See Appendix 5, Figure 3 for more

information). Sample diagrams demonstrating the sites of screening biopsies and Week 12 biopsies for a tumor is seen in Section 6.1.3.

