### 6.1.3 Intra-treatment Tissue Histopathologic Evaluation

All subjects will undergo intra-treatment Tissue Histopathologic Evaluation at Week 12 visit. For lesions that display complete clinical response, histologic presence or absence of tumor on biopsy determines whether or not the subject is eligible to end treatment early and enter the Observation period (See Appendix 5 , Figure 3). Subjects with clinical partial response or stable disease at Week 12 visit will continue treatment for the full duration of 24 week regardless of pathology on sampling biopsy (See Appendix 5, Figure 2).

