#### **Tumors Exhibiting Complete Clinical Response**

For lesions that the investigator has determined to show complete clinical response at Week 12 visit, sampling biopsy will be performed at the farthest edge(s) of pre-biopsy lesion compared to location of initial punch biopsy/biopsies at Pre-study Screening Visit (See Figure 1 A). Up to three 2-mm or three 3-mm punch biopsies will be performed on the area of tumor clearance at Week 12 when possible. Tumor biopsies may comprise no more than 10% of visible lesion seen at screening visit.

[figure not shown]

Figure 1. Site of Week 12 biopsies for tumors with exhibiting complete clinical response.

For lesions that display partial clinical response or stable disease by clinical response evaluation, “Residual Tumor Assessment” and “Area of Tumor Clearance Assessment” will be performed (See Figure 2.).

[figure not shown]

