**6.1.4 End of Treatment visit (Week 24)**

Any unused study drug will be collected.

After 24 weeks of treatment, all subjects will undergo sampling biopsy/biopsies. If residual histologic disease is detected, surgical excision will be performed within 4 weeks of last dose of study drug. If no histologic evidence of disease is observed, subjects will enter the observation period and be followed clinically every 3 months up to one year. (See Appendix 5, Figure 1 and Figure 2.)

Biopsies at Week 24 visit will be performed in similar manner as performed at the Week 12 visit.

For lesions that the investigator has determined to show complete clinical response at Week 24 visit, sampling biopsy will be performed at the farthest edge(s) of pre-biopsy lesion compared to location of initial punch biopsy/biopsies at Pre-study Screening Visit and sites of biopsies performed at Week 24 visit (See Figure 3). Up to three 2-mm or three 3-mm punch biopsies will be performed on the area of tumor clearance at Week 24 when possible. Tumor biopsies may comprise no more than 10% of visible lesion seen at screening visit.

[figure not shown]

Figure 3. Site of biopsies for tumors displaying clinical complete response at Week 24 visit.

For lesions that display partial clinical response or stable disease by clinical response evaluation, “Residual Tumor Assessment” and “Area of Tumor Clearance Assessment” will be performed (See Figure 4)

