## Subjects with complete clinical response and complete histologic response at Week 12 visit

	Pre-study Screening Visit	Treatment Initiation Visit	Visit 2	Visit 3	Visit 4	Observation Visit 1	Observation Visit 2	Observation Visit 3	Observation Visit 4
	Day 0	Baseline / Day 1	Week 4	Week 8	Week 12	Week 24	Week 36	Week 48	Week 60
Description									
Informed Consent	X								
Medical History	X								
Inclusion/Exclusion	X								
Concomitant medications	X	X	X	X	X	X	X	X	X
Physical exam	X	X	X	X	X	X	X	X	X
Vital signs	X	X	X	X	X	X	X	X	X
Height, weight	X	X	X	X	X	X	X	X	X
Target lesion identification	X								
Lesion measurement (pre-biopsy)	X								
Lesion measurement (post-biopsy)	X								
Lesion photography	X	X	X	X	X	X	X	X	X
Tumor margins and local landmarks map	X	X	X	X	X	X	X	X	X
Lesion punch biopsy/biopsies	X				X				
Urine Pregnancy Test	X 	X	X	X	X	X	X	X	X
CMP?CBC Tests	X	X 	X 	X 	X 				
Patient reported outcome questionnaires		X		X		X			
Review subject diary			X	X	X				
Study drug instructions		X	X	X	X				
Reminder to use effective measures to avoid pregnancy	X	X	X	X	X	X	X		
Administer study drug		X	X	X	X				
Adverse Events (AE) monitoring - PI and Oncologist		X	X	X	X	X	X	X	X

1. Two negative pregnancy tests with a sensitivity of at least 25 mIU/mL prior to starting medication. These tests must be at least 19 days apart. For patients with regular menstrual cycles, the second pregnancy test should be done during the first 5 days of the menstrual period immediately preceding the beginning of therapy and after the patient has used 2 forms of contraception for 1 month. For patients with amenorrhea, irregular cycles, or using a contraceptive method that precludes withdrawal bleeding, the second pregnancy test must be done immediately preceding the beginning of therapy and after the patient has used 2 forms of contraception for 1 month.
2. Repeat testing after screening test is at the discretion of the investigator as clinically determined
3. Post surgical subjects will be offered observational follow up as office visits or telephone visits

14.7            **APPENDIX 7: SKINDEX-16**

[http://www.proqolid.org/instruments/skindex\\_skindex\\_skindex\\_29\\_skindex\\_16](http://www.proqolid.org/instruments/skindex_skindex_skindex_29_skindex_16)

Thank you for participating in this study. We appreciate it. Please see below for instructions during your study participation.

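### The Week 12 stopping texts give opposite instructions for subjects with partial response or stable disease and tumor-free biopsies; the affected group is narrow, but the rule needs one wording

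*Combined protocol and SAP*

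**What the plan says.** Four places state who may stop at Week 12.

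- **Section 3 (Study Design).** Subjects are eligible to "discontinue treatment early and enter the Observation period if there is no histologic evidence of tumor on Week 12 pathology specimens". No clinical response is required, and the wording is permissive.
- **Section 6.1.2 (Interval Visits).** "For subjects with apparent clinical complete response at Week 12 and no histologic evidence of disease is observed, subjects will enter the observation period". Both conditions are needed, and the wording is mandatory.
- **Section 6.1.3.** "For lesions that display complete clinical response, histologic presence or absence of tumor on biopsy determines whether or not the subject is eligible to end" dosing before Week 24. Subjects with partial response or stable disease "will continue treatment for the full duration of 24 week regardless of pathology on sampling biopsy".
- **Appendix 6.** The schedule for Week 12 stoppers is headed "Subjects with complete clinical response and complete histologic response at Week 12 visit".

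Sections 6.1.2 and 6.1.3 also refer to figures in Appendix 5 for this decision. Those figures were not in the text available to me.

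**The concern.** Section 3 reads as a sufficient condition: tumor-free specimens alone open the way to Observation. Section 6.1.3 says that, for a lesion not in complete clinical response, pathology does not matter. For one kind of subject these are opposite instructions on whether treatment continues.

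The reading adopted affects several planned outputs for such a subject:

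- the time at which the End of Treatment lesion size is taken (Section 9.3.1.1);
- whether Week 24 histology exists (Section 9.3.1.2);
- whether the subject counts as completing 24 weeks (Section 9.3.3.2.2);
- how much exposure stands behind the 24-week safety objective (Section 2.2).

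**Working it through.** **1. The texts side by side**

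| Status at Week 12 | Section 3 | 6.1.2 Interval Visits | 6.1.3 | Appendix 6, Week 12 stoppers |
|---|---|---|---|---|
| Complete clinical response, biopsies negative | may stop | enters Observation | may stop | covered |
| Complete clinical response, biopsies positive | no early stop | no early stop | no early stop | not covered |
| Partial response or stable disease, biopsies negative | **may stop** | not among those who stop | **must continue** | not covered |
| Partial response or stable disease, biopsies positive | no early stop | no early stop | must continue | not covered |

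Only the third row is a conflict over stopping or continuing. The first row has a lesser conflict: stopping is optional in Section 3 and 6.1.3 but required in 6.1.2.

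**2. Can the third row occur?** Yes. Under 6.1.3, "For lesions that display partial clinical response or stable disease by clinical response evaluation, “Residual Tumor Assessment” and “Area of Tumor Clearance Assessment” will be" carried out. Sampling of the residual tumor may be a single 2-mm or 3-mm punch, and Week 12 biopsies may cover no more than 10% of the visible lesion. All specimens can therefore be negative while a lesion is still visible or palpable.

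**3. What happens to the data of such a subject who stops?** Section 6.1.4 says "After 24 weeks of treatment, all subjects will undergo sampling biopsy/biopsies", which does not reach a subject treated for 12 weeks. Section 6.1.5 applies the Week 24 procedures after early discontinuation for patient decision or progression, and negative histology is not listed. The Appendix 6 table for Week 12 stoppers marks biopsies at screening and Week 12 only, and its heading excludes this subject. That table is weak evidence by itself, because the other two Appendix 6 tables also mark no Week 24 biopsy although 6.1.4 requires one; that is a separate inconsistency.

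**4. Exposure.** 12 × 7 = 84 planned doses against 24 × 7 = 168. If k of n subjects stop at Week 12, mean planned treatment is 24 − 12k/n weeks. For k=1 this is 22.8 weeks at n=10 and 23.25 at n=16.

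**5. Response rates.** The plan's only precision figures (Section 9.1) are reproduced by p ± 1.96·√(p(1−p)/n):

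- n=16, p=0.75 (stated): 53.8% to 96.2%, against the plan's 54% to 96%.
- n=10, p=0.40 (implied by the midpoint, not stated): 9.6% to 70.4%, against the plan's 10% to 70%.

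One reclassified subject moves a rate by 1/n: 1/10 = 10 points, 1/16 = 6.25 points. These are ceilings, and both are well inside the half-widths of about 30 and 21 points.

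**6. How often?** Let q be the share of subjects in the third row. The documents do not give it, so the range below is an assumption. The expected number is 36q, and the chance of at least one is 1 − (1 − q)^36.

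| Assumed q | Expected of 36 | Chance of at least one |
|---|---|---|
| 2% | 0.7 | 52% |
| 5% | 1.8 | 84% |
| 10% | 3.6 | 98% |
| 30% | 10.8 | >99.9% |

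**The case against.** The strongest reply is that this is an overview sentence that leaves out a condition. Section 6.1 introduces its subsections as the detailed account of procedures. Sections 6.1.2 and 6.1.3 and the Appendix 6 heading agree with one another, and a subject with partial response stopped at Week 12 would fit no Appendix 6 schedule. Most sites would probably follow 6.1.3, and Appendix 5 may say the same. Much of this stands: the texts are not evenly split. But Section 6.1 contains no precedence clause, and Section 3 as written is not marked as incomplete. Whatever Appendix 5 shows, Sections 3 and 6.1.3 still disagree.

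A reader might infer three stronger points, which the documents do not support.

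- **That each affected subject shifts the response rate by 6 to 10 points.** Section 9.3.1.1 lists best overall response. If overall response means complete plus partial, as in the phase I result cited in Section 1.3 (17 + 2 of 33, or 58%), a partial responder at Week 12 already counts under either reading. The rate moves only if the response category changes after Week 12, for instance from stable disease to partial response or, in the category counts, from partial to complete. The Week 12 histology result is the same under both readings.
- **That treatment duration will differ between the two sites.** This is possible, but nothing shows that the sites read the texts differently, and Section 9 plans no between-site comparison.
- **That the missing rule for counting Week 12 stoppers at Week 24 follows from this contradiction.** It does not. Complete responders may stop at Week 12 under every text, so that gap exists whichever rule is kept.

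**Conclusion.** The inconsistency is real and narrow. It reverses the instruction only for subjects with partial response or stable disease whose Week 12 biopsies are all negative. For each of them it means 12 or 24 weeks of planned treatment (84 or 168 doses), with a different End of Treatment time, possibly no Week 24 histology, and a different completion status. The effect on a subtype response rate is at most 1/n per subject and may be zero. The optional-or-required conflict for complete responders with negative biopsies is lesser but also real.

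The contradiction itself rests on the text alone. Any count of affected subjects rests on an assumed q. I rate it as something that should be fixed: the rule governs stopping of treatment and the repair is cheap, but three of the four places already agree and the design does not depend on it.

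**What to change.** Reconcile Section 3, Section 6.1.2 (Interval Visits), Section 6.1.3 and Appendix 6 to a single Week 12 rule, and check the Appendix 5 figures against it. The rule should state the clinical condition, the histologic condition, and whether stopping is required or optional. If the adopted rule lets subjects with partial response or stable disease stop, they also need a visit schedule. Which rule to adopt is the sponsor's clinical decision.

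The cost is a few sentences in one amendment, with the agreement and IRB approval that Section 12.9 requires. Sample size and alpha do not change. How Week 12 stoppers enter the Week 24 analyses should be settled separately in Section 9, since it is open under any rule.
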